11.0 STUDY-SPECIFIC INSTRUMENTS

The following instruments will be employed to measure states of function, dementia, and movement. Copies of the instruments are provided in [Appendix 2](#).

- Mini-Mental State Examination ([MMSE](#))
- Patients' Global Impression of Change ([PGIC](#))
- Clinical Global Impression of Severity ([CGIS](#))
- Wechsler Adult Intelligence Scales, 4th edition ([WAIS-IV](#))

- Movement Disorder Society-Sponsored Revision of the Unified Parkinson's Disease Rating Scale ([MDS-UPDRS](#)).

12.0 STUDY-SPECIFIC PROCEDURES

12.1. Safety Assessments

Safety will be evaluated by monitoring for changes in the parameters summarized below, including any AEs/SAEs as reported by subjects or observed by the clinical staff, or using concomitant medication during the study.

12.1.1. Physical and Neurological Examination

A medically qualified professional will perform a physical examination that consists of a review of the major body systems (i.e., skin, head/ears/eyes/nose/throat (HEENT), cardiovascular, pulmonary, abdomen, musculoskeletal, and extremities) and a neurological examination which will include an assessment of cranial nerves, strength, coordination, reflexes, sensation, tremor, gait and mental status. Assessments of height, weight, and vital signs (systolic and diastolic blood pressure, pulse, temperature, and respiration) are included.

12.1.2. Electrocardiogram (ECG)

An appropriately qualified individual will conduct a standard 12-lead supine resting ECG. The ECG report must be reviewed, signed, and dated by the site PI (or a medically qualified individual delegated by the site PI). Those with clinically significant ECG findings will be referred for follow-up as deemed appropriate by the investigator and may be excluded from the study.

12.1.3. Clinical Laboratory Evaluations

Blood and urine samples will be obtained for clinical safety lab assessments as described in the Schedule of Events ([Appendix 1](#)). The following table lists the clinical safety lab tests that will be assessed by the central lab at these time points: the screening visit, each clinical visit (1 month, 2 months and 3 months), and the end of trial visit. Refer to the Laboratory Manual for additional details.

CLINICAL SAFETY LAB TESTS		
METABOLIC PANEL	COMPLETE BLOOD COUNT	URINALYSIS
Sodium (Na)	White Blood Cell Count (absolute and percentage): basophils, eosinophils, lymphocytes, monocytes, neutrophils	Color
Potassium (K)		Appearance
Chloride (Cl)		Specific Gravity
Carbon Dioxide (CO2)	Red Blood Cell Count (RBC)	pH
Blood Urea Nitrogen (BUN)	Hemoglobin (Hb)	Blood
Glucose	Hematocrit (HCT)	Glucose
Calcium (Ca)	Mean Corpuscular Volume (MCV)	Protein
Creatinine (Crn)	Mean Corpuscular Hemoglobin (MCH)	Ketones
Bilirubin (direct and Total)	Mean Corpuscular Hemoglobin Concentration (MCHC)	Leukocyte Esterase
Albumin	Red Blood Cell Distribution Width (RDW)	Nitrite
Protein - Total	Mean Platelet Volume (MPV)	Urobilinogen
Glutamic-Oxaloacetic Transferase (AST, SGOT)	Platelet Count (PLT)	Bilirubin (total)
Glutamic-Pyruvate Transferase (ALT, SGPT)		
Alkaline Phosphatase (ALP)		
eGFR (estimated Glomerular Filtration Rate)	Screening Only Hemoglobin A1C (HbA1c)	

Lab reports will be reviewed, signed, and dated by the site PI (or a medically qualified individual delegated by the PI). If a value is outside of the laboratory's normal range, the clinician will indicate if the value has clinical significance. Those results that are deemed clinically significant may need to be repeated and may require follow up with the subject's primary care physician for further evaluation.

12.2. Biofluids

12.2.1. Plasma for Biomarkers and Pharmacokinetics

Plasma samples will be collected at the baseline visit, and during the end of trial visit for analysis of biomarkers and PK, as described in the Laboratory Manual.

13.0 PERSONNEL REQUIREMENTS

The site PI is responsible for the overall conduct of the study at the site. The PI is to supervise project personnel and ensure that clinical raters maintain a high level of skill and accuracy in conducting assessments. Additionally, the PI will perform or supervise clinical evaluation of all subjects and ensure protocol adherence. Additional key personnel will be required, as outlined in the procedure manual.

14.0 ADVERSE EVENTS (AES)

14.1. Definition

An AE is defined as per the US Code of Federal Regulation, Title 21, Part 312.32 (2016) and ICH E2A: International Conference on Harmonization - Tripartite Guideline: Clinical Safety Data Management: Definitions and Standards for Expedited Reporting (1994).

Any untoward medical occurrence in a subject or clinical investigation subject administered a pharmaceutical product and which does not necessarily have to have a causal relationship with this treatment.

Collection of adverse events will begin once informed consent is signed and will continue until the 24-hour phone follow-up after the subject is discharged from the clinic at the end of study visit or discontinues from the study. Adverse events include but are not limited to: (1) worsening or change in nature, severity, or frequency of conditions or symptoms present at the start of the study; (2) Subject deterioration due to primary illness; (3) intercurrent illness; and (4) drug interaction. An abnormal laboratory value will only be reported as an AE if the investigator considers it clinically significant, or if it leads to the Subject being withdrawn from the study.

The investigator should attempt to establish a diagnosis of the event based on signs, symptoms, and or other clinical information. In such cases, the diagnosis should be documented as the AE and not the individual signs or symptoms. Symptoms and conditions present at the beginning of the study will be characterized, so that AEs can be defined as any new symptom, or any increase in frequency or severity of an existing symptom. Adverse events should be described with medical terminology so that the event can be matched against a medical coding dictionary, such as MedDRA (Medical Dictionary for Regulatory Activities).

Investigators should report their assessment of the potential relatedness of each AE to the protocol procedure, and to the investigational product, and/or drug delivery system used in the protocol.

Following questioning and evaluation, all AEs, whether determined to be related or unrelated to the study drug by a medically qualified site PI or clinician must be documented in the Subject's records, in accordance with the investigator's normal clinical practice, and on the AE electronic case report form (eCRF).

14.2. Following Up on AEs

The investigator is obliged to follow subjects with AEs until the events have subsided, the conditions are considered medically stable, or the subjects are no longer available for follow up. Subjects who discontinue due to adverse experiences will be treated and followed according to established medical practice. All pertinent information will be entered into the eCRF. Adverse events will be reported to the Medical Monitor, Sponsor, and DSMB, per Coordinating Center SOPs and the DSMB Charter.

15.0 SERIOUS ADVERSE EVENTS (SAE)**15.1. Definition**

An SAE is defined as per the US Code of Federal Regulation, Title 21, Part 312.32 (2016) and ICH E2A: International Conference on Harmonization - Tripartite Guideline: Clinical Safety Data Management: Definitions and Standards for Expedited Reporting (1994).

An adverse event or suspected adverse reaction is considered “serious” if, in the view of either the investigator or Sponsor, it results in any of the following outcomes: Death, a life-threatening adverse event, inpatient hospitalization or prolongation of existing hospitalization, a persistent or significant incapacity or substantial disruption of the ability to conduct normal life functions, or a congenital anomaly/birth defect. Important medical events that may not result in death, be life-threatening, or require hospitalization may be considered serious when, based upon appropriate medical judgment, they may jeopardize the subject and may require medical or surgical intervention to prevent one of the outcomes listed in this definition. Examples of such medical events include allergic bronchospasm requiring intensive treatment in an emergency room or at home, blood dyscrasias or convulsions that do not result in inpatient hospitalization, or the development of drug dependency or drug abuse.

15.2. Reporting SAEs

Collection of serious adverse events will begin once informed consent is signed (regardless of study drug exposure) and will be monitored throughout the trial. All SAEs must be reported to the Medical Monitor and the Sponsor within 24 hours of learning of the event. This in turn will trigger an alert to the appropriate Coordinating Center personnel and Protocol Project Directors, which will lead to the initiation of the creation of the report. A notification will be sent to all participating sites and the DSMB once the report is available. Sites will inform their IRB of the event based on local IRB requirements. The Sponsor is the IND holder and is responsible for submitting any SAEs according to the FDA reporting requirements. The Sponsor will work with the Coordinating Center personnel to submit any SAEs according to the EU local country requirements.

16.0 SUSPECTED UNEXPECTED SERIOUS ADVERSE REACTION**16.1. Definition**

A suspected unexpected serious adverse reaction (SUSAR) is an AE that is assessed as serious, related, and unexpected.

16.2. Reporting of Suspected Unexpected Serious Adverse Reactions

The Sponsor is responsible for informing the Competent Authority (CA), the European Medicines Agency and the IECs as well as the Regulatory Authority (RA), the FDA and IRB of any individual case reports of SAEs that are determined to be reportable by the Sponsor (SUSARs) in Europe and the US, respectively. The Investigator will ensure that all relevant information is provided to the Sponsor to allow the Sponsor to meet their obligations to report the SUSAR to the CA/RA and IEC/IRB. For a SUSAR that is fatal or life-threatening, this should be reported as soon as possible and not later than 7 days after the Sponsor was first advised, for any other SUSAR this should be within 15 days.

17.0 ADVERSE EVENTS OF SPECIAL INTEREST

Not applicable.

18.0 PRECAUTIONS/OVERDOSE

If a subject receives a dose exceeding 200 mg of buntanetap, the dose may be considered toxic. Since this is a double-blind study, if a subject swallows more than 10 capsules with the assumption of them being in the 20mg buntanetap group, this will be considered an overdose, and in such case, the information will be collected following the same timeframe and procedures as for a SAE, even if the overdose is not associated to any AE/SAE. No specific treatment is recommended apart from appropriate supportive measures.

19.0 PREGNANCY

Female subjects will be instructed to notify the Investigator immediately if they become pregnant during the study. Male subjects will be instructed to notify the Investigator immediately if their partner becomes pregnant. Pregnant subjects will be withdrawn from further study treatment. The subjects will also be instructed to report pregnancies discovered after the last visit, if they believe that conception occurred during their participation in the study.

A pregnancy as such is not an AE, unless there is a possibility that the IMP has interfered with the efficiency of any contraceptive measures. However, the Investigator should report pregnancies according to the procedures and timelines described for reporting of SAEs ([Section 15.2](#)). The pregnancy report form should be used instead of the SAE form.

The pregnant subject or partner will be followed until the end of the pregnancy. Any complication during the pregnancy should preferably be reported as an AE or SAE (if it fulfils SAE criteria).

The outcome of the pregnancy must be reported on the pregnancy report form. Any spontaneous abortion, stillbirth, birth defect/congenital anomaly, death, or other serious infant condition must be reported and followed up as an SAE.

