Definitive reproductive and developmental toxicity studies have not been conducted with buntanetap. As a result, women of childbearing potential will be excluded from participating in this study unless they agree to be on contraceptive for the whole duration of the trial and one month after. Female partners of male participants of childbearing potentials will also need to agree to be on contraceptive for the whole duration of the trial and one month after. Male study participants should not donate sperm and female study participants should not donate eggs during the whole duration of the trial and one month after.

At this time, there is no controlled clinical data available for anyone receiving SARS-CoV-2 (COVID-19) vaccination while being treated with buntanetap. However, based on the intended mechanism of actions and currently available data for these vaccine candidates and for buntanetap, it is not believed that there are specific risks to consider in subjects participating in this study who have received SARS-CoV-2 (COVID-19) vaccination or who are planning to receive the vaccination. As such, SARS-CoV-2 (COVID-19) vaccination is not prohibited. If appropriate, SARS-CoV-2 (COVID-19) vaccination should be considered as a concomitant medication (see Section 7.8.2).

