8.1. Inclusion Criteria

Subjects must meet the following criteria:

1. Diagnosis of idiopathic PD according to MDS Clinical Diagnostic Criteria for Parkinson's Disease ([Postuma 2015](#)).
2. H&Y score =1, 2 or 3 during ON-state & OFF-state <2hrs per day.
3. Male or female aged 40 – 85 years.
4. MMSE score between the range of 22-30 during screening visit (ON-state) and subjects can live independently without a caregiver.
5. Female subjects of childbearing potential* must have a negative urine pregnancy test at Screening, must be non-lactating and must agree to use a highly effective method of contraception (i.e., a method resulting in a failure rate of less than 1% per year when used consistently and correctly) during the trial and for 4 weeks after the last dose of trial treatment, such as:
 - Oral, intravaginal, or transdermal combined (estrogen plus progestogen) hormonal contraception associated with inhibition of ovulation
 - Oral, injectable, or implantable progestogen-only hormonal contraception associated with inhibition of ovulation
 - Intrauterine device (IUD)
 - Intrauterine hormone-releasing system (IUS)
 - Bilateral tubal occlusion
 - Vasectomized partner (a vasectomized partner is a highly effective contraception method provided that the partner is the sole male sexual partner of the participant, and the absence of sperm has been confirmed. If not, an additional highly effective method of contraception should be used)
 - Sexual abstinence (sexual abstinence is considered a highly effective method only if defined as refraining from heterosexual intercourse during the entire period of risk associated with the study treatment. The reliability of sexual abstinence needs to be evaluated in relation to the duration of the study and the preferred and usual lifestyle of the participant)

*Non-childbearing potential includes surgically sterilized or postmenopausal with no menstrual bleeding for at least one year prior to study start.

6. Male subjects must be sterile or sexually inactive or agree not to father a child during the study and one month after the last dose of study medication and must agree to use a barrier method for contraception. Female partners of male subject must adopt a highly effective method of contraception with a failure rate of less than 1% per year when used consistently and correctly such as:

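### Section 19.0's rule for reporting pregnancies found after the last visit stops short of the protocol's own post-dose contraception period, clearly so for female subjects who complete the study

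*Protocol*

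**What the plan says.** Protocol section 19.0 gives three instructions to subjects:

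- Women, while in the study: "Female subjects will be instructed to notify the Investigator immediately if they become pregnant during the study".
- Men: "Male subjects will be instructed to notify the Investigator immediately if their partner becomes pregnant". This sentence carries no time limit.
- After the last visit, subjects are also to "report pregnancies discovered after the last visit, if they believe that conception occurred during their participation in the study".

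The same section has the investigator report pregnancies on the SAE timeline, follow them to their end and report the outcome.

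The contraception periods are set elsewhere in the protocol:

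- Section 5.1 states that "Definitive reproductive and developmental toxicity studies have not been conducted with buntanetap". For that reason it excludes women of childbearing potential "unless they agree to be on contraceptive for the whole duration of the trial and one month after". It applies the same period to female partners of male participants and to sperm and egg donation.
- Section 8.1, criterion 5, requires highly effective contraception of female subjects "during the trial and for 4 weeks after the last dose of trial treatment".
- Section 8.1, criterion 6, requires male subjects to "agree not to father a child during the study and one month after the last dose of study medication".

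**The concern.** The sponsor chose to protect against conception for some weeks after dosing because reproductive toxicity data are incomplete. A conception in those weeks is one the protocol sought to prevent, so one would expect the subject to be told to report it. The rule for pregnancies discovered after the last visit instead turns on conception during participation. If participation ends with the last visit or the call a day later, almost all of the post-dose contraception period lies outside the rule.

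What is at stake is safety capture. Pregnancy reports are the only human reproductive safety information that these documents plan to collect, and the investigator's duties start only once a pregnancy is known. Power, type I error and the efficacy analyses are not involved.

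**Working it through.** **1. The protocol's own duration figure.** The synopsis gives total participation as 7-8 months, made up of screening of up to 42 days, baseline, 6 months at home and an in-clinic visit. Section 9.5 allows ±7 days on the last visit. With 365.25/12 = 30.44 days per month:

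- Last visit, full screening: 42/30.44 + 6 = 1.38 + 6 = 7.38 months (±7/30.44 = ±0.23, so 7.15 to 7.61).
- 24-hour call: 7.38 + 1/30.44 = 7.41 months (7.18 to 7.64).
- Adding 28 days after the last dose: 7.38 + 28/30.44 = 8.30 months (8.07 to 8.53).

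With full screening, the stated total is met without the post-dose weeks and exceeded with them. This supports the reading but does not settle it. With 14 days of screening the last visit falls at 14/30.44 + 6 = 6.46 months, below the stated range, and adding 28 days gives 7.38, inside it.

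**2. Where the text puts the post-dose weeks.**

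- The synopsis's description of participation ends with the in-clinic visit and lists no follow-up period.
- Section 9.5 makes the end of trial visit each subject's last clinical visit.
- Section 9.5.2 has the last dose given at that visit.
- Sections 5.1 and 8.1 name the trial (or study) and the weeks after it as two separate periods.

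Together these place the post-dose weeks outside participation, although no sentence defines when participation ends.

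**3. The gap for a completer.** Take the last dose at the last visit as day 0.

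- Last planned contact: about day 1 (section 9.5.3).
- End of contraception period: day 28 (four weeks) or about day 30 (one month).
- Gap: 28 − 1 = 27 days, or 30.44 − 1 = 29.4, about 29 days.

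**4. Does anything else close it?**

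- AE collection ends with the 24-hour call (section 14.1).
- SAE collection is described as running through the trial (section 15.2).
- The last scheduled pregnancy test is at the end of trial or early discontinuation visit (Appendix 1) and cannot detect a later conception.
- After the trial, care passes to the treating physician (section 9.5.4).
- The SAP has no pregnancy-reporting provision.

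**5. Size against the whole contraception window.** Six months is 6 × 30.44 ≈ 183 days. With 28 post-dose days the window is 211 days, and 27/211 = 13% of it is uncovered.

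**The case against.** Several objections have force.

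- **Participation is undefined.** Its end is inferred, and section 9.5 also uses end of trial for the last subject's last visit. A generous reader could stretch the wording to cover the weeks after dosing. That remains possible, but the sentence that applies after the last visit refers to the subject's own participation, and the passages above point away from the wider reading. Consent pages are not part of the text reviewed, so the wording given to subjects cannot be checked.
- **Partners.** A reader might infer that partner pregnancies conceived after the last dose are also outside the rule. The documents do not establish this. The sentence for male subjects has no time limit, and the later sentence adds a duty without clearly restricting the earlier one. The text is ambiguous for partners.
- **Follow-up to outcome.** A reader might infer that such pregnancies would not be followed. Section 19.0 does not say so. The conception condition sits only in the instruction to subjects, and the investigator's reporting and follow-up duties have no conception-date limit. Any pregnancy that is reported would be followed.
- **Exposure.** It is tempting to say that the protocol labels the post-dose weeks an at-risk period. It sets a contraception requirement; its phrase about a period of risk appears only in the definition of abstinence and has no stated length. Section 3.2 gives a half-life of 5 hours in plasma and more than 12 hours in CSF/brain. Five half-lives, the convention the protocol uses for prior investigational agents, would be about 25 hours and at least 60 hours (2.5 days). Exposure late in the gap may therefore be low. This is indicative only: half-lives at 5 and 10 mg could not be calculated accurately, and the protocol does not derive its window from them.
- **Early discontinuers.** Their discontinuation visit may fall some days after the last dose, which shortens their gap.

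These points narrow the finding. They do not remove the mismatch for female completers.

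**Conclusion.** The mismatch is real and modest. For female subjects who complete the study, a conception from about day 1 to day 28-30 after the last dose lies inside the required contraception period but triggers no instruction to report. The gap is about 27 to 29 days, or about 13% of the whole contraception window on the four-week figure. For early discontinuers it may be shorter, and for partners of male subjects it is unclear.

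The conclusion assumes that participation ends with the last visit or the call a day later, which is the natural reading but not a stated definition. Case numbers will be small at ages 40 to 85; the documents give no count of women of childbearing potential or of partners, so none is estimated here.

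**What to change.** Extend the condition in section 19.0 and keep its present coverage. A pregnancy discovered after the last visit would be reportable if conception is believed to have occurred during participation or before the end of the post-dose contraception period in section 8.1. State that this applies to female subjects and to partners of male subjects. Give the instruction at the end of trial visit, the early discontinuation visit and the 24-hour call.

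The present condition should not be swapped for one that starts at first dose. Participation includes screening, so a conception shortly before first dose is reportable now and would be lost.

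The sponsor should also reconcile four weeks and one month across sections 5.1, 8.1 and 19.0; which length applies is the sponsor's decision.

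The cost is one protocol sentence and a discharge reminder, with no added visit or test. SAP section 8.10.2 reports enrollment complete as of June 9, 2023, so if subjects have finished their visits, a letter asking sites about post-dose conceptions would serve the same purpose.
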